5.3. Pharmacokinetic Analysis Set

The pharmacokinetic analysis set (PKAS) will be the subset of subjects from the safety analysis set who provide at least one pharmacokinetic concentration.

5.4. Treatment Misallocations

If a subject was:

- Randomized but not treated: the subject will appear on the subject evaluation table as randomized but not treated; this is the extent of how much the subject will be reported;
- Treated but not randomized: the subject will be reported under the treatment they actually received for all safety analyses, but will not be included in the efficacy analyses;
- Randomized but took incorrect treatment: If a subject received the incorrect treatment for the whole duration of the study, then the subject will be reported under their randomized treatment group for all efficacy analysis, but will be summarized under the treatment they actually received for all safety analyses; if a subject received the incorrect treatment at only some dosing occasions then the subject will be reported under their randomized treatment group for both efficacy and safety analyses. If sufficient doses were incorrect

and therefore deemed a major protocol deviation, the subjects may be excluded as sensitivity analysis.

5.5. Protocol Deviations

The following sections describe any protocol deviations that relate to the statistical analyses. It is possible that unexpected deviations will arise, becoming known only after the study has been active for a long period of time; hence more deviations may be added. A full list of protocol deviations for the study report will be compiled prior to database closure.

5.5.1. Deviations Assessed Prior to Randomization

At screening phase prior to randomization, the investigator will assess and document subjects against the inclusion and exclusion criteria as set out in sections 4.1 and 4.2 of the protocol.

5.5.2. Deviations Assessed Post-Randomization

Post-randomization deviations include:

- Subjects who receive excluded concomitant medications or rescue medications during the treatment period as described in Section 5.8 of the Protocol;
- Subjects who were randomized but took incorrect treatment;
- Subjects not satisfying the eligibility criteria, although, not identified until after randomization occurred.

Any significant deviation or violations from the protocol will be reviewed by the clinical team during the course of the study and prior to database closure and a decision taken regarding evaluation for each analysis set.

6. ENDPOINTS AND COVARIATES

For all clinically planned measures, visits should occur within a window of the scheduled visit, which can be found in [Appendix 1](#).

6.1. Efficacy Endpoint(s), Health Outcome and Biomarkers

6.1.1. Primary Endpoint

- *Proportion of subjects achieving the IGA for clear (0) or almost clear (1) and 2 points improvement from baseline at Week 12. The baseline will be defined as the IGA score on Day 1 pre-dose.*

6.1.2. Secondary Endpoints

6.1.2.1. Efficacy Endpoints

6.1.2.2. Key Secondary Efficacy Endpoints

- *Percent change from baseline in the eczema area and severity index (EASI) Total score at Week 12.*

6.1.2.3. Secondary Efficacy Endpoints

- *Proportion of subjects achieving the IGA for clear (0) or almost clear (1) and ≥ 2 points improvement from baseline at all scheduled time points except Week 12.*
- *Percent change from baseline in the EASI total score at all scheduled time points except Week 12.*
- *Proportion of subjects achieving ≥ 3 points improvement in the pruritus numerical rating scale (NRS) from baseline at all scheduled time points.*
- *Proportion of subjects achieving ≥ 4 points improvement in the pruritus numerical rating scale (NRS) from baseline at all scheduled time points*
- *Time to achieving ≥ 3 points improvement in NRS*
- *Time to achieving ≥ 4 points improvement in NRS*
- *Percent change from baseline in the pruritus NRS from baseline at all scheduled time points.*
- *Proportion of subjects achieving ≥ 2 points improvement in the IGA from baseline at all scheduled time points.*
- *Proportion of subjects achieving a $\geq 50\%$, 75% and 90% improvement in the EASI Total score (EASI50, EASI75, EASI90) at all scheduled time points.*
- *Change from baseline in affected body surface area (BSA) at all scheduled time points.*
- *Change from baseline in SCORing atopic dermatitis (SCORAD) at all scheduled time points.*
- *Percent change from baseline in SCORing atopic dermatitis (SCORAD) at all scheduled time points.*
- *Proportion of subjects achieving a $\geq 50\%$ and 75% improvement in SCORAD (SCORAD50, SCORAD75) from baseline at all scheduled time points.*

6.1.2.4. Safety Endpoints

- *Incidence of treatment emergent adverse events.*
- *Incidence of specific clinical laboratory abnormalities (anemia, neutropenia, thrombocytopenia, lymphopenia, lipid profile, liver function tests [LFTs]).*

6.1.2.5. Patient Reported Outcome (PRO) Endpoints

- *Change from baseline in Pruritus NRS score at all scheduled time points.*

090177e18dabc776\0.1\Draft\Versioned On:07-Feb-2018 10:11 (GMT)

- *Proportion of subjects with patient global assessment (PtGA) of AD of clear (0) or almost clear (1) and ≥ 2 points improvement from baseline at all scheduled time points.*
- *Change from baseline in dermatology life quality index (DLQI) total score at all scheduled time points.*
- *Change from baseline in patient Oriented Eczema Measure (POEM) at all scheduled time points.*
- *Change from baseline in the hospital and anxiety depression scale (HADS) at all scheduled time points.*

6.2. CCI [REDACTED]

- CCI [REDACTED]
- [REDACTED]
- [REDACTED]

6.3. Covariates

For variables expressed as change from baseline, the baseline value will also be included in the analysis model as a covariate.

7. HANDLING OF MISSING VALUES

In general missing values will not be imputed for descriptive statistics.

7.1. Efficacy Data

[figure not shown]
For the binary efficacy data such as IGA response, subjects who receive at least one investigational product and discontinue from the study before Week 12 will be considered as non-responders (NR) for all subsequent visits during the treatment phase until Week 12.

For the continuous efficacy endpoints such as percent change from baseline in EASI score at Week 12, the observed case (OC) approach and the last efficacy observation carrying forward (LOCF) missing value imputation will both be considered. The efficacy endpoints will be set to missing after rescue treatment is used. The LOCF method will then be used to impute missing values.

7.2. Pharmacokinetic Concentrations and Biomarker Data

- **Concentrations outside the limit of quantification**

090177e18dabc776\0.1\Draft\Versioned On:07-Feb-2018 10:11 (GMT)

In summary statistics for pharmacokinetic and biomarker data, assayed values below the lower limit of quantification (LLOQ) will be set to zero. Other imputations (eg, ½ LLOQ) may also be considered in other analyses (eg, Pop-PK and PK/PD analyses), if deemed appropriate. In listings values below LLOQ will be reported as “<LLOQ” where LLOQ will be replaced with the numerical value for the lower limit of quantification. The LLOQ for various PK and biomarker concentrations will be noted in all tables and listings.

- **Missing concentrations**

If a concentration value is not collected or cannot be analyzed due to bad samples, it will be considered as missing data and will not be imputed.

- **Missing actual sampling time**

If actual sampling time (date or hour) value is missing, the protocol-stated nominal time will be used.

7.3. Patient Reported Outcomes (PRO) Data

Some of the analyses of PRO endpoints will be based on the OC data. If missing values happen at the item level within a PRO, the developer’s guideline on missing value imputation will be considered.

7.4. Safety Endpoints

Missing data for safety endpoints will not be imputed and will be left as missing. The follow-up period will be included for the safety endpoint. A sensitivity analysis maybe carried out excluding the follow-up period.

8. STATISTICAL METHODOLOGY AND STATISTICAL ANALYSES

All efficacy analyses described in this section will only apply to the data in the treatment period to the end of week 16 (Week 0 to 16).

Percentages will be presented to one decimal place in all summaries. Minimum and maximum values will be presented to the same number of decimal places as collected on the CRF or within the laboratory screening panel; mean and median will be presented to one further decimal place; standard deviation will be presented to two further places.

Whilst every effort has been made to pre-specify all analyses in this statistical analysis plan, should any additional exploratory analyses be found to be required after unblinding, the analyses and the reasons for them will be fully detailed in the clinical study report.

In all data presentations, results will be sorted by increasing dose level, starting with Placebo.

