3. STUDY DESIGN

This Phase 2b, multi-center, randomized, double-blind, 5-arm, parallel group study will enroll a total of approximately 250 subjects (providing approximately 200 completers, 40 subjects per treatment group). The study will be conducted at approximately 60 sites.

Figure 1. Study Design Schematic

090177e18dabc380\0.1\Draft\Versioned On:07-Feb-2018 09:59 (GMT)

Subjects who have chronic AD that has been present for at least 1 year (prior to screening visit) and affected BSA of $\geq 10\%$, EASI ≥ 12 and IGA ≥ 3 at the screening and baseline visits will be included in the study. Subjects must also have a documented history of inadequate response to treatment with topical medications given for at least 4 weeks, or for whom topical treatments are otherwise medically inadvisable (eg, because of important side effects or safety risks) within 12 months of the first dose of study drug. Subjects will be randomized to 1 of 4 treatment groups or placebo in the ratio of 1:1:1:1. Investigators, subjects, and the sponsor study team will be blinded as to treatment group.

Subjects will be screened within 35 days prior to the first dose of study drug to confirm that they meet the subject selection criteria for the study. There will be a 12-week double-blind treatment period as well as a 4-week follow up period.

An interim analysis may be performed when approximately a total of 110 randomized subjects complete 6 weeks of study or discontinue prematurely from study in order to assess the percent change of EASI score from baseline as well as other safety and efficacy endpoints such as IGA response as appropriate. Please refer to [Section 9.4](#) for details.

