Appendix 2. Diagnostic Criteria for Atopic Dermatitis

A subject is to have a clinical diagnosis of atopic dermatitis according to the criteria of Hanifin and Rajka.

Hanifin and Rajka's Diagnostic Criteria for Atopic Dermatitis

Major Criteria (must have at least three)

Pruritus

Typical morphology and distribution:

Adults: flexural lichenification or linearity

Children and infants: involvement of facial and extensor surfaces

Chronic or relapsing dermatitis

Personal or family history of atopy

Minor Criteria (must have at least three)

Xerosis

Ichthyosis/keratosis pilaris/palmer hyperlinearity

Immediate (type 1) skin test reactivity

Elevated serum IgE

Early age at onset

Tendency to skin infections (Staphylococcus aureus, herpes simplex)/impaired cellular immunity

Hand/foot dermatitis

Nipple eczema

Conjunctivitis

Dennie-Morgan fold

Keratoconus

Anterior subcapsular cataracts

Orbital darkening

Facial pallor/erythema

Pityriasis alba

Anterior neck folds

Itch when sweating

Intolerance to wool and lipid solvents

Perifollicular accentuation

Food intolerance

Course influenced by environmental/emotional factors

White demographic/delayed blanch

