8.1.3. Statistical Methods for Time_to_Event Variables

For time to event variables such as time to achieve NRS response, Kaplan-Meier analyses will be used to account for any right censoring, i.e., event not observed. Kaplan-Meier survival estimates and the number and percentage of subjects experiencing the relevant event or being censored will be summarized and plotted by treatment group. 90% CIs will be generated for the estimate of time to NRS response.

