8.2.2.2.2. Analysis of binary secondary endpoints

Unless otherwise stated, all primary analyses for the binary secondary endpoints are based on the FAS population with OC missing value imputation. Baseline is defined as the score for each assessment prior to the first dosing. These endpoints include:

Binary secondary endpoints include:

- *Proportion of subjects achieving the IGA for clear (0) or almost clear (1) and ≥ 2 points improvement from baseline at all scheduled time points except Week 12*
- *Proportion of subjects achieving ≥ 3 points improvement in the pruritus numerical rating scale (NRS) from baseline at all scheduled time points*
- *Proportion of subjects achieving ≥ 4 points improvement in the pruritus numerical rating scale (NRS) from baseline at all scheduled time points*
- *Proportion of subjects achieving ≥ 2 points improvement in the IGA from baseline at all scheduled time points*
- *Proportion of subjects achieving a $\geq 50\%$, 75% and 90% improvement in the EASI total score (EASI50, EASI75, EASI90) at all scheduled time points*
- *Proportion of subjects achieving a $\geq 50\%$ and 75% improvement in SCORAD (SCORAD50, SCORAD75) from baseline at all scheduled time points*

All binary secondary endpoints at each visit (except Week 12 for IGA response) will be analyzed in the same fashion as the primary endpoint using GLMM. In the case of convergence issues, logistic regression analysis at each time point with NR imputation will be performed.

For endpoint “Proportion of subjects achieving ≥ 3 points improvement in the pruritus numerical rating scale (NRS) from baseline at all scheduled time points”, subjects with baseline NRS ≤ 2 will be considered as non-responders.

For endpoint “Proportion of subjects achieving ≥ 4 points improvement in the pruritus numerical rating scale (NRS) from baseline at all scheduled time points”, only subjects with baseline NRS ≥ 4 will be analyzed.

Survival analysis will be performed for time-to-event data such as time to achieving ≥ 3 points improvement in NRS and time to achieving ≥ 4 points improvement in NRS as described in section 8.1.3.

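### The time-to-itch-response endpoints have no baseline-NRS condition and no end time, so they can include patients who cannot respond and count first responses seen off drug

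*SAP*

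**What the plan says.** **Period.** Protocol 3 states: "There will be a 12-week double-blind treatment period as well as a 4-week follow up period". The Schedule of Activities has dosing from Day 1 to Day 85, and SAP 7.1 ends the treatment phase at Week 12. SAP 8 nevertheless says that all efficacy analyses "will only apply to the data in the treatment period to the end of week 16 (Week 0 to 16".

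**Endpoints.** SAP 6.1.2.3 lists time to improvement of at least 3 and at least 4 NRS points. SAP 8.2.2.2.2 says "Survival analysis will be performed for time-to-event data such as time to achieving" these thresholds and refers to 8.1.3, where "Kaplan-Meier analyses will be used to account for any right censoring, i.e., event not observed". Section 8.1.3 gives summaries by arm with 90% confidence intervals. It names no at-risk population, censoring date, end time or between-arm test. SAP 8.2.2 makes the Full Analysis Set the default. The table in SAP 8.2.5 has no row for these endpoints.

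**Low baseline itch.** SAP 8.2.2.2.2 has two rules, both written for the proportion endpoints only. For 3 points, "subjects with baseline NRS ≤ 2 will be considered as non-responders". For 4 points, "only subjects with baseline NRS ≥ 4 will be analyzed".

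**Entry.** Patients who meet BSA, EASI and IGA levels "at the screening and baseline visits will be included in the study". Protocol 4.1 and 4.2 set no NRS minimum. Pruritus is one of four items under "Major Criteria (must have at least three" in Protocol Appendix 2, so the diagnosis does not require it.

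**The concern.** A patient with baseline NRS 0 to 2 cannot improve by 3 points, and one with 0 to 3 cannot improve by 4. The SAP deals with this for the response rates but not for the curves. On the curves such a patient would stay at risk until censored, as though a response were still possible. The 4-point curve and the 4-point response rate would then sit side by side in the report and describe different populations.

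The Week 16 window also lets an improvement first recorded off drug count as an event. An arm with fewer responders at Week 12 has more patients left who could have such an event, and that will usually be placebo. What is at stake is how clearly two secondary endpoints show the onset of itch relief. The primary analysis is not affected.

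**Working it through.** The documents give no event rate, sample size or power for these endpoints, so there is no planned figure to reproduce. The timing can be checked exactly. The size can only be illustrated.

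**1. Off-drug scores for completers.** Last dose is Day 85. NRS is scheduled at Day 99 (Week 14) and Day 113 (Week 16).
- 99 − 85 = 14 days and 113 − 85 = 28 days after the last dose.
- With the SAP Appendix 1 windows (Days 96–106 and 107–120): 96 − 85 = 11 to 120 − 85 = 35 days.
- At the longest repeat-dose mean half-life in Protocol 1.5 (5.0 h), Day 99 is 14 × 24 / 5.0 ≈ 67 half-lives after the last dose.

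The schedule grid and Protocol 6.3.1 list no NRS at Week 13, but the grid's NRS footnote refers to every visit. Those passages need to be reconciled.

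**2. Off-drug scores for early discontinuers.** Protocol 6.4 moves patients who stop treatment into follow-up, with the first visit 1 week after the last dose. SAP Appendix 1 assigns visits by days since first dose. Suppose a patient stops at Day 29 and the follow-up visits keep their nominal spacing. NRS would then fall near Day 29 + 14 = 43 and Day 29 + 28 = 57, inside the Week 6 and Week 8 windows. For these patients an off-drug event can come before Week 12. The non-responder rule in SAP 7.1 is written for binary data and for leaving the study, so it does not clearly cover them.

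**3. Share unable to respond (assumed).** Take baseline NRS as a rounded normal variable with mean 6.5 to 7.5 and SD 1.8 to 2.2. A rounded score below 4 means an underlying value below 3.5.
- Mean 7.5, SD 1.8: Φ((3.5 − 7.5)/1.8) = Φ(−2.22) ≈ 1.3%.
- Mean 6.5, SD 2.2: Φ((3.5 − 6.5)/2.2) = Φ(−1.36) ≈ 8.6%.

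That is roughly 1% to 9%, or 0.5 to 4.5 of 50 patients per arm (250/5). For the 3-point endpoint (cut at 2.5) the same inputs give about 0.3% to 3.5%.

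**4. Dilution from these patients.** Let f be the share unable to respond, equal across arms in expectation. Observed difference = (1 − f) × difference among those able to respond. For a 40-point difference:
- f = 1%: 0.99 × 40 = 39.6 points.
- f = 9%: 0.91 × 40 = 36.4 points.

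**5. Off-drug events.** Let pC and pT be the Week 12 response among those able to respond, and q the share of remaining non-responders who first respond off drug, equal in both arms. Week 16 response is p + (1 − p)q, so the difference becomes (1 − q)(pT − pC). With pC = 30%, pT = 60% and q = 10% (all assumed):
- Placebo: 30 + 70 × 0.10 = 37%. Active: 60 + 40 × 0.10 = 64%. The difference is 27 points instead of 30.
- First seen off drug: 7/37 = 19% of placebo responders and 4/64 = 6% of active responders.

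Adding f = 5% gives 0.95 × 0.90 × 30 = 25.7 points. If q differs by arm, the difference still shrinks while 40qT < 70qC, that is, while qT is less than 1.75 times qC.

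**6. What does not move.** A Kaplan-Meier estimate at time t uses only events and censoring up to t. Completers' events at Weeks 14 and 16 leave the curve to Week 12 unchanged. They alter the tail, the counts of events and censored patients, and a median only where fewer than half have responded by Week 12.

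**The case against.** The Week 16 horizon comes from a general sentence, not from 8.1.3, so this is mainly a gap in specification. The endpoints are secondary, have no planned between-arm test, fall outside the multiplicity control in SAP 4.2.2 and feed no decision rule. Randomisation balances low-itch patients in expectation, so the result is dilution rather than false benefit. All of this stands, and it limits the weight of the point.

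A reader might infer that SAP 8 should be cut to Week 12 for all efficacy analyses. The documents do not support that. SAP 8.2.2.1 runs the IGA sensitivity model over all visits including follow-up, and the table in 8.2.5 marks follow-up as included for every endpoint it lists. A global cut would contradict both.

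A reader might also want the 3-point response-rate rule replaced by a baseline restriction. That is a preference: the SAP states the rule explicitly, and it is conservative. A patient kept on the 3-point curve without an event is close to its equivalent.

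Simply censoring at the last on-drug score is not free of cost. The sample-size text plans for 20% dropout. If some patients stop for lack of benefit, such censoring credits them with the later response chance of those who stay.

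**Conclusion.** The concern holds as a gap in specification with a modest consequence. As written, the curves can include patients unable to reach the threshold and can count first responses seen off drug. For completers this happens at Weeks 14 and 16; for early discontinuers it may happen before Week 12. Only the 4-point pair has a clear population mismatch.

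The expected effect is mainly a smaller apparent difference, confined to event counts, the tail and late quantiles, except for what early discontinuers add before Week 12. The size rests on assumptions: 39.6 to 36.4 points from a true 40 if 1% to 9% start below 4, and a further factor (1 − q) at Week 16.

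It would go too far to say that the trial does enrol patients who cannot respond, since no baseline NRS distribution is given. It would also go too far to assume dilution at 10% or 20% of patients, which lies outside the range derived here, or to say that the whole curve is distorted.

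**What to change.** In SAP 8.1.3 and 8.2.2.2.2 only:

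- **Population.** Analyse time to a 4-point improvement in subjects with baseline NRS of 4 or more, matching the response rate. For time to a 3-point improvement, state that subjects with baseline NRS of 2 or less stay in without an event, matching the existing rule for the proportion. Alternatively, show the subset with baseline NRS of 3 or more as a supplement.
- **Events and end time.** Count only on-treatment NRS scores as events and end the curves at the Week 12 visit.
- **Early discontinuers.** Keep those without an event as non-responders to Week 12, in line with SAP 7.1. Add censoring at the last on-drug NRS as a sensitivity analysis, noting that it may be informative.

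In SAP 8, correct only the label, to *treatment and follow-up periods (Week 0 to 16)*. Leave the planned by-visit follow-up analyses in place, marked as off-drug.

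The cost is slightly fewer subjects in one secondary endpoint and one extra sensitivity analysis. The subset is defined by a pre-dose score, so the randomised comparison is kept.

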8.1. Statistical Methods

The following sub-sections contain the descriptions of the methods that will be used in the analysis of the various endpoints in this study. The choice of analysis method will be

090177e18dabc776\0.1\Draft\Versioned On:07-Feb-2018 10:11 (GMT)

dependent on the endpoint of interest (eg whether the endpoint is a primary, key secondary or exploratory endpoint or whether the endpoint is efficacy or safety). The analysis methods to be used for each endpoint will be covered in [Section 8.2.5](#).

